### 3.2 Secondary Endpoints:

- Change in FEV1
- Radiographic improvement in sarcoidosis lung disease by frontal chest x-ray. Local investigators will score chest x-rays. This analysis correlates roentgenographic findings with physiologic parameters.
- Change in 6 minute walk distance, oxygen saturation and level of dyspnea.
- Change in the Saint George's Respiratory Questionnaire (SGRQ; King's Sarcoidosis Questionnaire (KSQ) for the assessment of health status; The Fatigue Assessment Scale (FAS).
- Necessity of escalating immunosuppressive therapy secondary to continued clinical deterioration, after study enrollment.
- Safety profile of regimen as evidenced by adverse events and abnormal lab values, tolerability and toxicity of the treatment regimen including comparison of reported adverse events and abnormal laboratory values compared to placebo.
- Increase in T cell biologic function through normalization of p56Lck and IL-2 expression.
- Decrease in peripheral and pulmonary T cell responses against ESAT-6 at 16 weeks compared to baseline.

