### **5.3 Study Drug Dosing and Administration:**

The following oral CLEAR medications or matching placebo will be introduced as follows:

Day 0 Start: Azithromycin: 250mg po QD (or 500 3 days/week if toxicity) x 8 weeks *and*  
Ethambutol: 1200 mg po QD for  $\geq 50$ kg; <50kg 800 mg po QD (or 3 days/week if toxicity) x 8 weeks  
Rifampin 600 mg QD or Rifabutin 300mg po QD (or 3 days/week if toxicity) x 16 weeks  
Levaquin: 500 mg po QD (or 3 days/week if toxicity) x 16 weeks

Participants will be allowed to take their regimen three times/week instead of daily (which has been shown to be equally efficacious) if toxicity occurs that is thought to be drug related. In addition, if toxicity warrants, one or more drugs can be discontinued and the participant can continue to participate.

The site PI may also elect to stagger the start of study drugs to help identify which drugs may be eliciting which side effects. The study drugs would be introduced starting with Azithromycin and Ethambutol at the baseline visit (day 0) and introducing Rifampin (or Rifabutin) the following week (day 7), and Levaquin one week later (day 14) using the same dosages as above.

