## 7. Statistical Considerations

### 7.1 Statistical Methods

#### 7.1.1 Analysis of Primary Endpoint

The comparison between CLEAR and placebo arms will be made using the Students's t-test. Normality of the primary endpoint will be examined using Kolmogorov-Smirnov test. If normality is violated, the comparison between CLEAR and placebo arms will be made using the Wilcoxon rank sum test.

The primary endpoint of this study is the arithmetic difference between %FVC predicted value measured at baseline and week 16 for each patient randomized. For analysis purposes, we define the week 16 post-randomization %FVC predicted value measurement at the value closest to 16 weeks from randomization within a window of 12 weeks to 20 weeks from randomization. This more accurately represents the data collected at 16 weeks on study due to the variability of visit schedules resulting from staggering the start of study drugs and patient scheduling. To understand the trajectory of improvement with CLEAR therapy, we will also be measuring the %FVC predicted value at weeks 4 and 8. If the improvement is linear in time, the rate of improvement (slope of change) may be reported as a secondary endpoint in the study.

This analysis is an exploratory analysis. Mixed effect models will be used to analyze these repeated measures with a random subject effect and with the treatment (CLEAR versus placebo) and the time trend (baseline, week 4, week 8, and week 16) as fixed effects. For the error covariance, we will use autoregressive model of order 1 [AR(1)] or other plausible covariance structures. The focus of this study will be the treatment effect and the time trend of the endpoint; however, mixed effect models also provide the flexibility of controlling for and evaluating covariates such age, race, and gender.

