#### 7.1.2 Approaches to the Analysis

The following 2 approaches will be used for the analyses:

- **Intention-to-Treat** All patients with a post-treatment endpoint measurement will be included. This will be considered the primary analysis and performed for all endpoints.
- **Per Protocol** This will be performed as a secondary analysis for the primary endpoint only. A patient who is identified as a major protocol violator will not be included. Protocol violators will be considered as follows: 1) Realize that patient did not meet Inclusion Criteria after enrolled into study; 2) Find an Exclusion criteria after enrolled into the study; 3) Regimen was

permanently stopped before 4 weeks; 4) Exacerbation requiring greater than 2 weeks of prednisone escalation. Major protocol violators will also be defined based on criteria that will be identified prior to unblinding the database.

**7.1.3 Multiplicity:** Since there is only 1 primary comparison for 1 primary endpoint for each study aim, and other comparisons are secondary and supportive, no multiplicity adjustment will be applied.

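### Section 7.1.1 lets the FVC slope become a secondary endpoint depending on how the observed course looks, which allows selective reporting

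*Combined protocol and SAP*

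**What the plan says.** The primary endpoint is the change in FVC percent predicted from baseline to week 16, compared by t-test or by Wilcoxon test if normality fails (section 7.1.1). The same section introduces the earlier visits: "To understand the trajectory of improvement with CLEAR therapy, we will also be measuring the %FVC predicted value at weeks 4 and 8". It continues: "If the improvement is linear in time, the rate of improvement (slope of change) may be reported as a secondary endpoint in the study". The following paragraph opens: "This analysis is an exploratory analysis". It describes a mixed model with a random subject effect, "with the treatment (CLEAR versus placebo) and the time trend (baseline, week 4, week 8, and week 16) as fixed effects". No treatment-by-time term is named.

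Section 3.2 lists the secondary endpoints, beginning with "Change in FEV1". The FVC slope is not among them. Section 7.1.3 says that "other comparisons are secondary and supportive, no multiplicity adjustment will be applied". The section on analysis of secondary endpoints applies the primary endpoint's methods to continuous secondary endpoints.

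**The concern.** The slope has two labels in consecutive sentences, and which one applies is decided by the data. The plan does not say how linearity is tested, what threshold applies, whether CLEAR, both arms or the difference is judged, or when and by whom. Even if the condition is met, reporting the slope as a secondary endpoint is optional. An endpoint admitted on those terms is not pre-specified support for the primary result, which is the role section 7.1.3 gives to secondary comparisons.

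The direction of any distortion depends on what the condition means. It speaks of an improvement being linear, directly after a sentence about improvement with CLEAR. Read literally, a flat or falling CLEAR course would not qualify, and the slope would then be promoted only when CLEAR looks good.

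A non-linear course is a realistic outcome. Section 5.3 gives "Azithromycin: 250mg po QD (or 500 3 days/week if toxicity) x 8 weeks", with ethambutol also for 8 weeks, while the rifamycin and levofloxacin run for 16. Sites may also stagger starts to days 7 and 14. Exposure therefore changes within the period that one slope would summarise, so the condition could decide the matter either way.

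**Working it through.** **Inputs from the documents.** SD of change 7.7, target difference 5 points, 51 completers per arm, 90% power, 20% dropout (section 7.3); 1:1 allocation (section 7.2); visits at weeks 0, 4, 8 and 16 (section 7.1.1).

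**Assumptions.** Two-sided 5% level, normal errors, the covariance between visits, and every specific version of the linearity rule. The documents give none of these.

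**1. The plan's own figure.** The normal approximation gives n = 2 × (1.960 + 1.282)² × 7.7² / 5² = 49.8, so 50 per arm. The exact t calculation gives 51 (power 90.1% at 51, 89.5% at 50). Then 51 / 0.80 = 63.75, so 64 enrolled. The figure is reproduced at two-sided 5%; one-sided 5% gives 41 and does not match. The plan gives no figure for the slope.

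**2. Closed form for the mildest improvement rule.** Suppose there is no true effect and the slope is reported only when the CLEAR slope is positive. Let Zc and Zp be the independent standardised arm slopes, with D = (Zc − Zp)/√2. Take the SE of the 16-week difference as 7.7 × √(2/51) = 1.52 points.

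- Mean: E[D | Zc > 0] = √(2/π)/√2 = 0.564, and 0.564 × 1.52 = 0.86 points in favour of CLEAR.
- False positives for CLEAR: P(D > 1.96 | Zc > 0) = 2 × (0.025 − 0.025²/2) = 0.049, against 0.025 without selection.

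**3. Simulation of alternative rules.** 200,000 trials per scenario, 51 per arm, SD of 16-week change 7.7. Three covariances were used: random intercept with independent errors, AR(1) with correlation 0.8 per 4 weeks, and random slope. Entries are for the reported between-arm slope difference, in points over 16 weeks; ranges are across the covariances.

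| Assumed rule | Reported (true 0) | Mean (true 0) | False positives for CLEAR (true 0) | Mean (true 5) |
|---|---|---|---|---|
| Always report | 100% | 0.00 | 2.5% | 5.00 |
| Lack-of-fit test for linearity at 5% | 95% | 0.00 | 2.5% | 5.00 |
| R² > 0.9 in CLEAR, either direction | 5–14% | about 0 | 7–8% | 5.08–5.20 |
| Linear and CLEAR slope positive | 47–48% | 0.82–0.86 | 4.9% | 5.00 |
| CLEAR slope positive and R² > 0.9 | 3–7% | about 1.6 | 13–15% | 5.08–5.20 |
| Significant CLEAR improvement and linear | 2.3–2.4% | 2.4–2.5 | 33–34% | 5.01 |

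The second row shows no bias because, under normal errors, the departure from linearity is independent of the efficient slope estimate. The third row shows that a fit measure that grows with the slope raises the two-sided error among reported slopes to 13–15%, split evenly between directions. Bias towards CLEAR under no effect appears only where the rule also requires CLEAR to improve.

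**4. The contrast itself.** With treatment and a linear time trend as the only fixed effects, both arms share one slope. With visits as categories there is no slope at all. In neither case does the named model contain a between-arm difference in rate, so the quantity that might be promoted is undefined. Promotion would also leave the method unclear, because the mixed model applies to the exploratory analysis and the primary endpoint's test applies to continuous secondary endpoints.

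**The case against.** The condition can be read as an ordinary caveat about model adequacy: do not summarise FVC by one slope unless a line fits. The dosing schedule supports such caution, and a formal linearity check leaves the slope difference unbiased. This stands. It justifies checking the fit; it does not justify letting the check decide endpoint status.

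Three stronger readings are tempting and not supported.

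- A reader might infer that the slope, whenever reported, is biased towards CLEAR. The text does not establish this. The bias needs an added requirement that CLEAR improves, which the wording permits but does not fix. A one-sided 5% significance threshold on the CLEAR slope alone would give about 2.2 points and 25% false positives for CLEAR under no effect, but no such threshold is in the documents, and under no effect it would be met in only 5% of trials.
- A reader might infer that only a favourable version would ever be seen. The week-16 comparison and the exploratory mixed model are planned whatever the trajectory, FVC is collected at every visit (section 6.8), and the listed secondary endpoints are untouched.
- A reader might infer that linearity is to be judged on unblinded data. The plan does not say when, by whom or on which arms.

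It is also fair to say that secondary comparisons are already described as supportive, so the consequence is limited.

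**Conclusion.** The point holds as one of pre-specification. Section 7.1.1 makes the slope's status depend on the observed course and on discretion, contradicts itself on the label, and departs from the list in section 3.2. That allows selective reporting.

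The size of any distortion depends on a rule that the plan does not state. It is nil for a pure linearity check. Under no true effect it is about 0.8 to 0.9 points, with 4.9% false positives for CLEAR against 2.5%, if a positive CLEAR slope is also needed; it reaches about 2.5 points under the strictest rule simulated. With the planned 5-point effect it is at most about 0.2 points under every rule tried. These figures rest on the assumed level, normal errors and covariances. They describe slopes that get reported; the error rate over all trials and the primary week-16 test are unaffected. This is a cheap improvement, not a threat to the main conclusion.

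**What to change.** Replace the conditional sentence in section 7.1.1 with text such as:

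> The difference between arms in the rate of change of FVC percent predicted over 16 weeks is an exploratory analysis. It will be estimated from a treatment-by-time term in the mixed model and reported with its 95% confidence interval whatever the observed shape or direction, beside the differences between arms at weeks 4, 8 and 16. Any check of linearity will describe model fit only and will not decide reporting or endpoint status.

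Also add the treatment-by-time term to the list of fixed effects. With time in weeks, its coefficient is the between-arm slope difference; with visits as categories, it supports the visit-specific differences.

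The exploratory label agrees with the sentence that follows in section 7.1.1 and leaves section 3.2 unchanged. Listing the slope in section 3.2 now, with its method, would also remove the dependence on the data, but would need more editing.

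The cost is a few sentences, with no new visits, data or participants. The sponsor gives up the option to promote the slope after seeing the data.

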#### 7.1.4 Missing Data Analyses

Every effort will be made to avoid missing data. Still, we plan to enroll 64 subjects per arm to achieve 51 completed subjects, as described in the Sample Size Justification. For missing data, we will explore the missing data mechanism whether it is missing completely at random, missing at random, or missing not at random. We will test whether missingness on the primary endpoint depends on covariates and whether the missing data mechanism is ignorable. After a good understanding about the missing data mechanism, we will adopt two strategies to deal with missing data. The multiple imputation method that incorporates predictive mean matching and flexible additive imputation models as implemented in the *aregImpute* function in the Hmisc package (Harrell, 2013, page 12) in R will be used. We will also conservatively impute missing data to perform sensitivity analyses. Imputing strategies could be last-value-carry-forward (we believe this imputation is conservative since subjects on placebo may get worse and subjects on CLEAR may get better if they stayed in the study, and we assume a flat carry-forward) or we could assume a spontaneous improvement rate for the placebo arm estimated from the non-missing data if that is observed. The primary analysis is the intention-to-treat (ITT) analysis of the complete data set. These additional analyses that deal with missing data are secondary and they are to corroborate study findings from the primary ITT analysis.

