### 7.3 Sample Size Justification

Sample size is calculated for primary endpoint; change from baseline of FVC percent predicted. Using data from 34 participants treated with Bosentan to treat pulmonary hypertension, we obtained the SD of 7.7 for the primary endpoint. We need a sample size of 51 completed participants per arm to have 90% power to detect a 5% difference (5% in CLEAR vs. 0% in placebo) in change of FVC percent predicted from baseline. To factor in a 20% dropout rate, we plan to enroll 64 subjects per arm. This brings the sample size to 128 participants. In the Phase I trial, we experienced a higher drop rate 30%, but review of the clinical data demonstrates that patients with advanced disease accounted for the majority of the study withdrawals. The Phase II trial will allow patients to drop one study drug, and will include a research nurse coordinator to encourage study participation. We anticipate that we will have not have as high a study withdrawal rate.

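### The exploratory mixed model for %FVC has no treatment-by-time term, so it cannot give a CLEAR-specific trajectory or slope, or the effect on change

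*Combined protocol and SAP*

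**What the plan says.** Section 7.1.1 makes the primary analysis a t-test (or Wilcoxon rank sum test) on each patient's change in %FVC predicted from baseline to week 16. It then describes a further, exploratory analysis of the repeated measurements:

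- Purpose: "To understand the trajectory of improvement with CLEAR therapy, we will also be measuring the %FVC predicted value at weeks 4 and 8".
- Possible endpoint: "If the improvement is linear in time, the rate of improvement (slope of change) may be reported as a secondary endpoint in the study".
- Model: "Mixed effect models will be used to analyze these repeated measures with a random subject effect", with "treatment (CLEAR versus placebo) and the time trend (baseline, week 4, week 8, and week 16) as fixed effects".
- Covariance: "For the error covariance, we will use autoregressive model of order 1 [AR(1)] or other plausible covariance structures".

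The section adds that attention will be on the treatment effect and the time trend, and that covariates such as age, race and gender can be included. No interaction between treatment and time is mentioned.

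Two other sections show what the plan expects the arms to do. Section 7.3 sizes the trial to "detect a 5% difference (5% in CLEAR vs. 0% in placebo) in change of FVC percent predicted from baseline". The section on missing data analyses reasons that "subjects on placebo may get worse and subjects on CLEAR may get better if they stayed in the study".

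**The concern.** Baseline is one of the four time levels, so the response in this model is the %FVC level, not the change. With treatment and time as the only fixed effects, two things follow whatever the variances are:

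- The fitted change from baseline to any visit is the same in both arms.
- The treatment coefficient is a constant gap between arms, averaged over visits that include baseline.

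Neither quantity is the effect on change, and neither is a rate of improvement with CLEAR. The plan expects the arms to diverge, and the model as written does not let them.

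This is the model given for the repeated %FVC data, and its slope may be reported as a secondary endpoint. Readers could take the treatment term for the effect on FVC change, or the common slope for the improvement with CLEAR. Section 7.1.4 on secondary endpoints applies the primary endpoint's methods to continuous secondary endpoints. If that is read to include this model, FEV1 and walk distance have the same problem.

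**Working it through.** **Inputs from the documents (section 7.3).** Week-16 effect 5 points (5 in CLEAR, 0 in placebo); SD of change 7.7; 51 completers per arm; 64 per arm after 20% dropout.

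**Assumed, because not given.** Two-sided alpha 0.05; between-patient SD of %FVC at a single visit 10 to 20; AR(1) correlation φ between successive visits 0 to 0.6, on top of a random intercept; complete data; four shapes for how the effect develops.

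**The plan's own figure.** The exact two-sided t-test has power 89.5% with 50 per arm and 90.1% with 51, so 51 is reproduced. Dropout: 51/0.8 = 63.75, so 64. The sample size stands.

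**Expected treatment term without interaction.** It is a weighted mean of the visit-specific arm differences. With φ = 0 each of the four visits has weight 1/4. With AR(1) by visit order, the first and last visits have weight 1/(2 + 2(1−φ)) and the middle two (1−φ)/(2 + 2(1−φ)). At φ = 0.6 these are 1/2.8 = 0.357 and 0.4/2.8 = 0.143.

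For linear growth the differences at weeks 0, 4, 8 and 16 are 0, 1.25, 2.5 and 5:

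- φ = 0: (0 + 1.25 + 2.5 + 5)/4 = 2.19
- φ = 0.6: 0.143 × (1.25 + 2.5) + 0.357 × 5 = 2.32

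| Shape (true week-16 effect 5 in each) | Differences at weeks 0, 4, 8, 16 | Treatment term, φ = 0 | Treatment term, φ = 0.6 |
|---|---|---|---|
| Linear | 0, 1.25, 2.5, 5 | 2.19 | 2.32 |
| Half at week 4, full by week 8 | 0, 2.5, 5, 5 | 3.13 | 2.86 |
| Full by week 4 | 0, 5, 5, 5 | 3.75 | 3.21 |
| Week 16 only | 0, 0, 0, 5 | 1.25 | 1.79 |

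**Precision of that term.** At φ = 0 the residual variance is 7.7²/2 = 29.6, the random-intercept variance is SD² − 29.6, and SE = √[(2/51)(intercept variance + 29.6/4)].

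- SD 10: √[(2/51)(70.4 + 7.4)] = 1.75
- SD 20: √[(2/51)(370.4 + 7.4)] = 3.85

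Over φ from 0 to 0.6 the range is 1.75 to 3.88. Power (normal approximation) runs from 6% (week 16 only: 1.25/3.85 = 0.32 SEs) to 57% (full by week 4: 3.75/1.75 = 2.15 SEs).

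**With treatment-by-visit added.** The week-16 contrast in change has expectation 5.0 for every shape. Its SE is 7.7 × √(2/51) = 1.52 and its power about 91%.

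**Simulation check** (SD 15, φ = 0.4, linear, 5,000 runs). Treatment term: mean 2.29, SD 2.83, power 12%. Week-16 change contrast: mean 5.04, SD 1.53.

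**Common slope.** With 1:1 allocation and linear trends, the shared time slope is the mean of the two arm slopes. Each row below has the same 5-point difference between arms.

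| True change over 16 weeks, CLEAR / placebo | Common slope per 16 weeks | Slope difference with interaction |
|---|---|---|
| +5 / 0 | (5 + 0)/2 = +2.5 | 5.0 |
| +2.5 / −2.5 | 0.0 | 5.0 |
| 0 / −5 | −2.5 | 5.0 |

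The SE of the slope difference is about 1.5.

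**Chance baseline imbalance, no treatment effect.** One SE of imbalance is SD × √(2/51), that is 10 × 0.198 = 2.0 to 20 × 0.198 = 4.0 points. The expected treatment term is then 1.5 to 3.8. The week-16 contrast in change moves by −0.3 to −0.6 only, through regression to the mean: 2.0 × 29.6/100 = 0.6 and 4.0 × 29.6/400 = 0.3.

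**The case against.** The strongest reply is that the sentence summarizes a model and is not a formula. It names the factors and never says main effects only. An analyst who wanted the CLEAR trajectory would probably add the interaction unprompted. That may well be so, but the text lists the fixed effects and names the treatment effect and the time trend as separate targets. Its only stated flexibility on the fixed effects concerns covariates. An independent analyst following it would fit the additive model.

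Second, the effect on change is already estimated by the primary t-test, and the mixed model is labelled exploratory. Both points are correct, and they limit the consequence: the primary inference and the sample size do not depend on this model.

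Third, a slope endpoint could be computed per patient and compared by t-test under the rule for continuous secondary endpoints, which would separate the arms. That would work, but the plan does not describe it; the only method set out for the repeated measurements is the mixed model.

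Fourth, much of the arithmetic uses assumed variances, correlations and shapes. This also stands. With AR(1) on actual weeks, for example, the linear-growth range becomes 2.2 to 2.5 rather than 2.2 to 2.3. The direction does not depend on these choices, because without an interaction the fitted change is identical in both arms. Nor does the plan claim any power for this model; the power figures show what the coefficient would be worth and do not contradict a stated number.

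**Conclusion.** The concern holds. As written, the model cannot show a trajectory or slope specific to CLEAR, and its treatment term does not estimate the effect on change. For a true week-16 effect of 5 points, that term would be expected to show between a quarter (1.25) and three quarters (3.75) of it, depending on when the effect appears, with low power. The common slope could be positive, zero or negative for one and the same treatment effect. These sizes rest on the plan's effect, SD of change and number of completers, together with the assumed between-patient SD, AR(1) correlation and effect shapes. The structural conclusion needs none of those assumptions. Because the model is exploratory and the primary t-test is untouched, this should be corrected in the SAP but does not threaten the main result.

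**What to change.** In section 7.1.1, add a treatment-by-time interaction with visit as a categorical factor, and name the week-16 contrast in change from baseline as the estimate to report. Baseline can stay in the response, preferably with the arm means constrained equal at that visit, or be moved to a covariate for the post-baseline values. If a linear trend is used and a slope reported, report the difference in slopes between arms from a treatment-by-linear-time term. If AR(1) is kept, define it on actual time, because visits at 0, 4, 8 and 16 weeks are unequally spaced.

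The cost is a revised SAP paragraph and a few lines of code. No new data are needed, and the primary analysis and sample size do not change.
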